16.2. Ethical Conduct of the Trial

This study will be conducted in accordance with and with the following:

- The Clinical Trial Protocol
- Ethical principles derived from international guidelines including the Declaration of Helsinki and Council for International Organizations of Medical Sciences (CIOMS) International Ethical Guidelines
- Applicable ICH Good Clinical Practice (GCP) Guidelines.
- Current and applicable laws and regulations.

The Investigator will be responsible for:

- Providing oversight of the conduct of the study at the site and adherence to requirements of 21 CFR, ICH guidelines, the IRB/IEC, European regulation 536/2014 for clinical studies, as applicable, and all other applicable local regulations.

16.3. Informed Consent Process

It is the responsibility of the Investigator (or a person designated by the Investigator when accepted by local regulations) to give each individual (or his/her legally authorized representative) full and adequate explanation regarding the nature of the study (e.g., objectives, aims, methods and procedures of the study, anticipated benefits, possible risks and potential hazards involved). The Investigator or his/her delegate will answer all questions regarding the study.

Participants must be informed that their participation is voluntary and that they have the right to withdraw from the study at any time.

Participants or their legally authorized representative will be required to sign before any trial-related procedure is undertaken, a statement of informed consent (ICF) that meets the requirements of ICH guidelines, 21 CFR 50 and Health Insurance Portability and Accountability Act (HIPAA) requirements, where applicable, local regulations, and the IRB/IEC or study center.

The medical record must include a statement that written informed consent was obtained before the participant was enrolled in the study and the date the written consent was obtained. The authorized person obtaining the informed consent must also sign the ICF.

Participants must be re-consented to the most current version of the ICF(s) during their participation in the study.

A copy of the signed ICF(s) must be provided to the participant or the participant's legally authorized representative.

16.4. Personal Data Protection

Participants will be assigned a unique identifier by the Sponsor. Any participant records or datasets that are transferred to the Sponsor or designee will contain the identifier only; participant names or any information which would make the participant identifiable will not be transferred.

The participant must be informed that his/her personal study-related data will be used by the Sponsor or designee in accordance with local data protection law. The level of disclosure must also be explained to the participant.

The participant must be informed that his/her medical records may be examined by Clinical Quality Assurance auditors or other authorized personnel appointed by the Sponsor or designee, by appropriate IRB/IEC members, and by inspectors from Regulatory Authorities.

17. SPONSOR DISCONTINUATION CRITERIA

Nerviano Medical Sciences reserves the right to discontinue the trial prior to inclusion of the intended number of patients but intends only to exercise this right for valid scientific or administrative reasons. After such a decision, the Investigator must contact all participating patients. As directed by Nerviano Medical Sciences or the Delegated Party, all study materials must be collected and all case report forms completed to the greatest extent possible.

18. DISSEMINATION AND PUBLICATION OF RESULTS

Results of the study may be presented or published. The conditions regulating dissemination of the information derived from this clinical study are described in the Clinical Trial Agreement.

Appendix 1. ECOG Performance Status

Grade	ECOG Performance Status
0	Fully active, able to carry on all pre-disease performance without restriction.
1	Restricted in physically strenuous activity but ambulatory and able to carry out work of a light or sedentary nature, e.g., light house work, office work.
2	Ambulatory and capable of all selfcare but unable to carry out any work activities; up and about more than 50% of waking hours.
3	Capable of only limited selfcare; confined to bed or chair more than 50% of waking hours.
4	Completely disabled; cannot carry on any selfcare; totally confined to bed or chair.
5	Dead

Appendix 2. Child Pugh Score and Classification

Child Pugh Score			
Measure	1 point	2 points	3 points
Total bilirubin, μ mol/l (mg/dl)	<34 (<2)	34-50 (2-3)	>50(>3)
Serum albumin, g/dl	>3.5	2.8-3.5	<2.8
PT INR	<1.7	1.70-2.30	>2.30
Ascites	None	Mild	Moderate to severe
Hepatic encephalopathy	None	Grade I-II (or suppressed with medication)	Grade III-IV (or refractory)

Chronic liver disease is classified into Child_Pugh class A to C, employing the added score from above.

Child-Pugh Classification	
Points	Class
5-6	A
7-9	B
10-15	C

Appendix 3. Contra-indicated drugs

The following lists are not intended to be exhaustive lists [27-28]. For updated interaction information please refer to drug summary of product characteristics. Investigators should verify case by case.

No strong inducers of FMO1 and FMO3 are currently known; they are contraindicated as a theoretical rule.

Sensitive CYP3A4 substrates	
CYP3A4	
Sensitive substrates*	Alfentanil, Avanafil, Budesonide, Buspirone, Conivaptan, Darifenacin, Darunavir, Dasatinib, Dronedarone, Ebastine, Eletriptan, Eplerenone, Everolimus, Felodipine, Ibrutinib, Indinavir, Lomitapide, Lovastatin, Lurasidone, Maraviroc, Midazolam, Naloxegol, Nisoldipine, Quetiapine, Saquinavir, Sildenafil, Simvastatin, Sirolimus, Tacrolimus, Ticagrelor, Tipranavir, Tolvaptan, Triazolam, Vardenafil

* Substrates metabolized at least at 80% by CYP3A4

CYP3A	
Substrates with NTI	Alfentanil**, Atemizole, Cisapride, Cyclosporine, Dihydroergotamine, Fentanyl, Pimozide, Quinidine, Sirolimus**, Tacrolimus**, Terfenadine.

** also sensitive CYP3A4 substrates

No BCRP substrates with NTI are currently known; they are contraindicated as a theoretical rule.

FDA, Drug Development and Drug Interactions: Table of Substrates, Inhibitors and Inducers

Appendix 4. Concomitant treatments to be used with caution

The following lists are not intended to be exhaustive lists [27-28]. For updated interaction information please refer to drug summary of product characteristics. Investigators should verify case by case.

No strong inhibitors of FMO1 and FMO3 are currently known.

Moderate sensitive CYP3A4 substrates	
CYP3A	
Moderate substrates*	Alprazolam, Aprepitant, Atorvastatin, Colchicine, Eliglustat, Rilpivirine, Rivaroxaban, Tadalafil

* Substrates metabolized from 50% to 80% by CYP3A4.

BCRP	
Substrates with no NTI	Atorvastatin, Hematoporphyrin, Imatinib, Pitavastatine, Rosuvastatin, Sofosbuvir, Sulfasalazine, Tizanidine

FDA, Drug Development and Drug Interactions: Table of Substrates, Inhibitors and Inducers

Appendix 5. The Distribution of Active Bone Marrow in the Adult

Site	Marrow Weight (g)	Fraction Red Marrow - Age 40	Red Marrow Weight -Age 40 (g)	% Total Red Marrow
Head				
Cranium	165.8	0.75	136.6	
Mandible	16.4	0.75	124.3	
			12.3	
Upper Limb Girdle			86.7	
2 Humerus, head & neck	26.5	0.75	20.0	
2 Scapulae	67.4	0.75	50.5	
2 Clavicles	21.6	0.75	16.2	
Sternum	39.0	0.6	23.4	2.3
Ribs			82.6	
1 pair	10.2	All 0.4	4.1	
2	12.6		5.0	
3	16.0		6.4	
4	18.6		7.4	
5	23.8		9.5	
6	23.6		9.4	
7	25.0		10.0	
8	24.0		9.6	
9	21.2		8.5	
10	16.0		6.4	
11	11.2		4.5	
12	4.6		1.8	
Vertebrae (Cervical)			35.8	3.4
1	6.6	All 0.75	5.0	
2	8.4		6.3	
3	5.4		4.1	
4	5.7		4.3	
5	5.8		4.4	
6	7.0		5.3	
7	8.5		6.4	
Vertebrae (Thoracic)			147.9	14.1
1 pair	10.8	All 0.75	8.1	
2	11.7		8.8	
3	11.4		8.5	
4	12.2		9.1	
5	13.4		10.1	
6	15.3		11.5	
7	16.1		12.1	
8	18.5		13.9	
9	19.7		14.8	
10	21.2		15.9	
11	21.7		16.3	
12	25.0		18.8	
Vertebrae (Lumbar)			114.1	10.9
1 pair	27.8	All 0.75	20.8	
2	29.1		21.8	
3	31.8		23.8	
4	32.1		24.1	
5	31.4		23.6	
Sacrum	194.0	0.75	145.6	13.9
Lower limb girdle			273.0	26.1
2 os coxae	310.6	0.75	233.0	
2 femoral head & neck	53.0	0.75	40.0	
Total	1497.7		1045.7	100.0

R.E. ELLIS - The Distribution of Active Bone Marrow in the Adult. Phy. Med. Biol. 5, 255 – 258, 1961.

Appendix 6. Recommended Effective Contraception

Since NMS-01940153E has potential induction of CYP3A4, hormonal contraceptives might lose efficacy while on treatment with NMS-01940153E and therefore this should specially be taken into account for female patients. It is advisable, unless total abstinence is applied, to use two contraceptive methods, of which at least one barrier method.

Methods that can achieve a failure rate of less than 1% per year when used consistently and correctly are considered as highly effective birth control methods and therefore recommended. Such methods include:

- combined (estrogen and progestogen containing) hormonal contraception associated with inhibition of ovulation:
 - oral
 - intravaginal
 - transdermal
- progestogen-only hormonal contraception associated with inhibition of ovulation:
 - oral
 - injectable
 - implantable
- intrauterine device (IUD)
- intrauterine hormone-releasing system (IUS)
- bilateral tubal occlusion
- vasectomy
- sexual abstinence

In case of male patients who have not had a vasectomy, the partner with a childbearing potential should use one of the highly effective contraceptive methods reported above.

Signature Page for MPSA-153-001-00667 v10.0

Reason for signing: Approved

Reason for signing: Approved

Reason for signing: Approved

Signature Page for MPSA-153-001-00667 v10.0

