**Calculated using the Cockcroft-Gault equation (mL/min): $(140 - \text{age}) \times \text{weight (kg)} / (\text{serum creatinine [mg/dL]} \times 72)$ for males. (For females multiply by 0.85)

10. In case of active hepatitis B (HBV) or chronic HIV infection the patient should receive antiviral therapy per local standard of care.
11. Patients must use effective contraception or abstinence. Female subjects must be surgically sterile or, if subjects of childbearing potential, must agree to use effective contraception (see [Appendix 6](#)) or abstinence during the period of therapy and in the following 180 days after discontinuation of study treatment. Male subjects must be surgically sterile or must agree to use effective contraception or abstinence during the period of therapy and in the following 90 days after discontinuation of study treatment.
12. With the exception of alopecia, resolution of all acute toxic effects of any prior systemic therapy, surgery or radiotherapy to NCI CTC (Version 5.0) Grade ≤ 1 or to the baseline laboratory values as defined in Inclusion Criteria Number 9.

13. Able and willing to comply with scheduled visits, therapy plans, and laboratory tests required in this protocol.
14. Signed and dated IEC-approved Informed Consent Form indicating that the subject is aware of the neoplastic nature of his/her disease and has been informed of the procedures to be followed, the investigational nature of the therapy, potential benefits, side effects, discomforts, risks and alternative treatments.

Subject Exclusion Criteria: The presence of any of the following will exclude a subject from study enrollment:

1. Known fibrolamellar HCC or mixed hepato-cholangiocarcinoma.
2. Subjects with untreated or incompletely treated gastro-esophageal varices with bleeding or at high risk for bleeding are excluded with the following clarification: subjects with history of prior variceal bleeding must have been treated with adequate endoscopic therapy without any evidence of recurrent bleeding for at least 6 months prior to study entry and must be stable on optimal medical management (e.g. non-selective beta blocker, proton pump inhibitor) at study entry.

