**Calculated using the Cockcroft-Gault equation (mL/min): $(140 - \text{age}) \times \text{weight (kg)} / (\text{serum creatinine [mg/dL]} \times 72)$ for males. (For females multiply by 0.85)

10. In case of active hepatitis B (HBV) or chronic HIV infection the patient should receive antiviral therapy per local standard of care.
11. Patients must use effective contraception or abstinence. Female subjects must be surgically sterile or, if subjects of childbearing potential, must agree to use effective contraception (see [Appendix 6](#)) or abstinence during the period of therapy and in the following 180 days after discontinuation of study treatment. Male subjects must be surgically sterile or must agree to use effective contraception or abstinence during the period of therapy and in the following 90 days after discontinuation of study treatment.
12. With the exception of alopecia, resolution of all acute toxic effects of any prior systemic therapy, surgery or radiotherapy to NCI CTC (Version 5.0) Grade ≤ 1 or to the baseline laboratory values as defined in Inclusion Criterion Number 9.
13. Able and willing to comply with scheduled visits, therapy plans, and laboratory tests required in this protocol.
14. Signed and dated IEC-approved Informed Consent Form indicating that the subject is aware of the neoplastic nature of his/her disease and has been informed of the procedures to be followed, the investigational nature of the therapy, potential benefits, side effects, discomforts, risks and alternative treatments.

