13. Radiation therapy within 4 weeks or radionuclide treatment (e.g., I-131 or Y-90) within 6 weeks before treatment start.
14. Untreated uncontrolled bacterial, viral, or fungal infections including acute HIV infection or acquired immunodeficiency syndrome (AIDS), untreated uncontrolled HBV, untreated uncontrolled HCV, untreated uncontrolled concomitant HBV and HCV; patients who are seropositive following HBV vaccine are eligible.
15. Subjects under treatment with therapeutic dose of anticoagulants (e.g., warfarin or warfarin-related agents, low-molecular weight heparin, or similar agent such as anti Xa and anti-thrombin agents) or antiplatelet agents (e.g. clopidogrel) or with coagulation disorders. Aspirin at dose up to 100 mg is permitted. Prophylaxis with anticoagulants is allowed to meet the INR value range as cited in inclusion criterion 9.
16. Uncontrolled diabetes mellitus.
17. Pregnant or breast-feeding women.

18. Known second malignancy that is progressing or requiring active treatment. Exceptions include adequately treated basal cell or squamous cell skin cancer or in situ carcinoma of the cervix uteri.
19. Current enrollment or participation in another interventional clinical trial.
20. Clinically significant respiratory or metabolic diseases uncontrolled by medication.
21. Subjects with active alcohol and/or substances abuse.
22. Any known organ dysfunction, serious illness, acute or chronic medical or psychiatric condition, or laboratory abnormality which, in the Investigator's opinion, may increase the risk associated/interfere with study participation, or with the interpretation of the results.
23. Subjects who, within 7 days prior to the first NMS-01940153E intake, are receiving or received strong inducers of FMO1 and FMO3.
24. Subjects who are receiving sensitive CYP3A4 substrates, CYP3A4 and BCRP substrates with narrow therapeutic index (NTI).

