9.2.7.5. Other Permitted Concomitant Medications

Therapies considered necessary for the patient's wellbeing may be given at the discretion of the Investigator, i.e. chronic treatments for concomitant medical conditions, as well as agents required for life-threatening medical problems, analgesics etc. according to the drug-drug interaction information. In particular, strong inhibitors of FMO1 and FMO3, moderate substrates of CYP3A4 and CYP3A4/BCRP substrates with no NTI should be used with caution (see [Appendix 4](#)).

Precaution should be used in treatment of NMS-01940153E with concomitant drugs that are known to prolong QT or QTc intervals, since the potential effect of study drug on QT prolongation has not been fully evaluated in humans. The Investigator should consult individual labels for concomitant medication. If medically indicated, a cardiology consult should be obtained.

Whenever possible the administration of drugs that may cause drug-drug interaction should not be done concomitantly with NMS-01940153E.

Patients should be advised to contact the treating physician before starting any new drug.

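### Appendix 6 warns that hormonal contraceptives might fail on NMS-01940153E but only advises a barrier method, so criterion 11 can be read as met by a hormonal method alone

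*Protocol*

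**What the plan says.** Protocol Appendix 6 opens with an interaction warning. NMS-01940153E may induce CYP3A4, so "hormonal contraceptives might lose efficacy while on treatment with NMS-01940153E", and "this should specially be taken into account for female patients". It then gives its remedy: "It is advisable, unless total abstinence is applied, to use two contraceptive methods, of which at least one barrier method".

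The next paragraph introduces a list of recommended methods by their reliability: "Methods that can achieve a failure rate of less than 1% per year when used consistently and correctly". Combined hormonal contraception (oral, intravaginal, transdermal) and progestogen-only contraception (oral, injectable, implantable) are on that list, with no condition attached. The last sentence of the appendix sends the partners of non-vasectomised male patients to the same list.

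The eligibility rule is inclusion criterion 11, in Sections 1.5 and 6.1. It begins "Patients must use effective contraception or abstinence". For women who are not surgically sterile it says "if subjects of childbearing potential, must agree to use effective contraception", refers to Appendix 6, and allows abstinence instead. The obligation runs through treatment and for 180 days afterwards. The criterion states neither how many methods are needed nor which type.

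**The concern.** The protocol identifies a specific way in which contraception could fail on this drug, and leaves optional the one measure that answers it. The list then rests on a failure rate below 1% per year, a figure that the preceding warning puts in doubt for hormonal methods taken with this drug. A site could follow the mandatory wording and still dose a woman whose only protection is a method that the protocol says might not work.

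What is at stake is embryo-fetal exposure. Section 9.1.3 calls the drug cytotoxic. Section 3.4 reports that it was negative in the Ames test but induced micronuclei in human lymphocytes in vitro, as its mechanism would predict. The 180-day contraception period and the exposure-in-utero reporting in Section 11.5.1.10 show that the protocol takes this risk seriously. This is a participant-safety matter; nothing statistical depends on it.

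**Working it through.** The plan gives no figure to reproduce. The check compares the texts, then bounds how many patients could be concerned.

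**1. What is mandatory and what is advice**

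| Source | Content | Force |
|---|---|---|
| Criterion 11 (Sections 1.5, 6.1) | Effective contraception with reference to Appendix 6, or abstinence | Mandatory; number and type of methods not stated |
| Appendix 6, first paragraph | Hormonal methods might lose efficacy; two methods, at least one a barrier | Advice |
| Appendix 6, list | Methods with failure below 1% per year | Recommendation; hormonal entries unconditional |

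Pointing a mandatory criterion at advice does not by itself make the advice mandatory. A woman using only a listed hormonal method is using something the appendix recommends.

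**2. The list**

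- Hormonal: 3 combined + 3 progestogen-only = 6.
- Hormone-releasing intrauterine system: 1. Whether the warning covers it is not stated.
- Non-hormonal: intrauterine device, tubal occlusion, vasectomy, abstinence = 4.
- Total 6 + 1 + 4 = 11 entries.

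**3. Other rules that might bar hormonal-only use**

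- Exclusion 24 bars sensitive CYP3A4 substrates and those with a narrow therapeutic index. The lists in Appendices 3 and 4, which are stated not to be exhaustive, name no hormonal contraceptive.
- Section 9.2.7.5 is not a prohibition: "Whenever possible the administration of drugs that may cause drug-drug interaction should not be done concomitantly with NMS-01940153E".
- Exclusion 22 lets the investigator exclude a patient for added risk, but does not require it here.
- Pregnancy tests detect a conception and do not prevent one.

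None of these makes a barrier method mandatory.

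**4. Exposure between tests in Phase II**

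Tests fall on day 1 of each cycle before dosing, and doses on days 1, 8 and 15 (Table 4, footnotes 9 and 19). After a true negative on day 1, two doses (days 8 and 15) precede the next scheduled test. It is three only if a conception was too early to detect on day 1. The interval is 28 days, or up to about 42 with the maximum delay, but the delay adds no doses.

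**5. How many patients**

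Phase I has ended (Section 5.3), so the reach is Phase II. Section 3.1 gives a 2.4:1 male-to-female ratio for the disease in general; that it holds in this trial is an assumption.

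- Women among 40 patients: 40 / (2.4 + 1) = 11.8.
- Women among 43 patients: 43 / 3.4 = 12.6.

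The share of these women who are of childbearing potential and rely on a hormonal method alone is not in the documents. For assumed shares:

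| Assumed share of women | Of 40 patients | Of 43 patients |
|---|---|---|
| 0% | 0 | 0 |
| 5% | 0.6 | 0.6 |
| 10% | 1.2 | 1.3 |
| 20% | 2.4 | 2.5 |

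The only median age given for patients on this drug is 58.5 years (Section 3.5, first-in-human study, mixed solid tumours). That points to the low end of the table.

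**The case against.** The strongest reply is that the risk has not been missed. Appendix 6 names the interaction, directs it at female patients and states the remedy, so the dispute is about how strongly that remedy is worded. This stands, and it limits the weight of the point.

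A reader might infer that the protocol plainly permits hormonal-only use. The documents do not support so firm a reading. Criterion 11 demands effective contraception and points to an appendix that opens by doubting hormonal methods on this drug. An investigator could fairly conclude that a hormonal method alone is not effective here. The text is open to both readings, and that ambiguity is the defect.

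A reader might also treat the hormonal entries, or the lack of a barrier method on the list, as an error. Neither is. The list also serves partners of male patients, who do not receive the drug, and the barrier method is named in the paragraph above as part of the advised pair.

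Other protections exist. Appendices 3 and 4 ask investigators to check each drug individually, Section 8.2 has the Sponsor verify eligibility, pregnancy is an exclusion, and in-utero exposure is followed up. These lower the practical risk without settling the question. The consent pages and the Study Manual were not available, so contraception instructions there cannot be ruled out.

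**Conclusion.** The point holds as an ambiguity in a safety rule. The appendix warns about hormonal methods, only advises the barrier that would answer the warning, and lists those methods without condition. Criterion 11 can then be read as satisfied by one of them alone.

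The number of Phase II patients affected is unknown, probably very small and possibly zero. The range of 0 to about 2.4 in 40 rests on the general disease sex ratio and on assumed shares of 0% to 20% with no basis in the documents; it is an illustration and not an estimate. The enzyme induction is described only as potential, with no size given. It would go too far to say that contraception is shown to fail on this drug, or that the trial's results are at risk: no endpoint, analysis set or sample size depends on this. What justifies acting is the imbalance between a possibly irreversible harm to a pregnancy and a small change of wording. It is worth making and does not need an amendment of its own.

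**What to change.** Keep the existing two-method advice, so that women using non-hormonal methods lose nothing, and keep the list for partners of male patients. Add this requirement to Appendix 6 and to criterion 11 in both Section 1.5 and Section 6.1:

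*While on treatment, a female patient of childbearing potential who uses a hormonal method must also use a barrier method; otherwise she must use one of the listed non-hormonal methods or abstinence.*

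State in Appendix 6 whether the hormone-releasing intrauterine system counts as hormonal for this purpose.

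The change can be bundled with the next protocol amendment. It costs IRB/IEC approval (Section 16.1), possible re-consent if the consent form changes (Section 16.3), and a minor burden for the few women who use a hormonal method. Visits, procedures, sample size and analyses stay as they are.
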